- ❖ Our previous studies have clearly showed the need for quantitative real time polymerase chain reaction (qRealTime-PCR) analysis performed on mucosal samples not only for its better diagnostic accuracy in comparison to *in situ* hybridization (ISH) and immunohistochemistry, but mostly in order to stratify the patients, since a positive result does not necessarily imply that the patient is suffering from an EBV-related end-organ disease (35). Indeed, we identified a cutoff of 1000 copies/100.000 cells as the value to distinguish a superimposed viral colitis from a pure relapse of the underlying disease (35). Furthermore, since no efficacious therapy is currently available for symptomatic EBV infection, the only possible intervention consists of a quick tapering and then discontinuation of steroids, while improving malnutrition if present. By contrast, the immunosuppressive and biological agents could be continued by virtue of their long-lasting effects. We also suggested a note of caution in prescribing steroids and biologics in those patients carrying a mucosal viral load of between 100 and 1000 copies, who should be closely monitored, while no modification of the standard treatment is needed for those with a mucosal viral load lower than 100 copies (36). In this regard, it should be emphasized that the search for circulating class M specific anti-virus antibodies is rather ineffective in detecting an active disease, since elevated levels can persist for up to two years after infection, while immunocompromised patients may not mount an IgM response (37).
- ❖ In addition, our evidence of localization of virus infection in colocytes represents the first step towards understanding the mechanisms of viral dissemination and the role of the lytic phase in tissue damage (24). Indeed, a suggested viral tropism to sites of inflammation, and its

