The **control group consists of 100 sex- and age-matched subjects**, selected in the same Center, undergoing colonoscopy with mucosal sampling as diagnostic workup for IBS in order to exclude macroscopic or microscopic disorders, or because alarm features are present: aged > 45-50 years, anemia, family history of colon cancer. That are confirmed to be suffering from IBS (C1), functional constipation/diarrhea (C2, C3) and functional abdominal bloating/distension (C4), following the Rome IV criteria (48), and who were not taking drugs possibly affecting immune response (steroids, immunosuppressant and biological agents) and microbiota composition (antibiotics, probiotics, prebiotics, proton pump inhibitors).

In addition, a small cohort of patients (n=20) suffering from **microscopic colitis** will be also enrolled as pathological control group (49).

All enrolled patients and controls undergo lower endoscopy with mucosal sampling and laboratory tests as diagnostic workup for their condition:

- Patients with active UC undergo colonoscopy and laboratory tests according to International guidelines and depending on physician judgement: active UC patients will undergo colonoscopy at baseline and laboratory tests at baseline, and at 3 and 6 months. A number of these patients, according to medical judgment, undergo medical examination at 9 and 12 months, and laboratory tests and colonoscopy at 12 months as optional follow-up. This is why the aim of the study is calculated at 6 months, but adding the optional follow-up at 9 and 12 months, will aid to understand if patients with superimposed EBV colitis undergo colectomy more frequently than patients without EBV colitis
- Patients with UC in remission undergo colonoscopy and laboratory tests as standard follow-up of their pathological condition according ECCO-ESGAR guidelines [52] (ex: to evaluate mucosal healing or screening)
- Patients with IBS undergo colonoscopy and laboratory tests only if alarm features are present (age > 45-50 years, anemia, family history of colon cancer, weight loss, blood mixed with stool).

Each enrolled case will undergo clinical and/or laboratory examination as standard follow-up of his/her pathological condition. All the laboratory tests are shown in the Appendix 5.

Each patient and control give written informed consent after approval by the local Bio-Ethics Committee is obtained.

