- ❖ Quantitation of EBV and HCMV DNA. For each patient and control, the EBV and HCMV load will be assessed in terms of International Units (IU) on both freshly collected whole peripheral blood samples and endoscopic specimens harvested from colonic mucosa, by qRealTimePCR technique as previously reported (51). Specifically, in the IBD group, two snap-frozen biopsies will be taken from either inflamed and/or non-inflamed mucosa as assessed during the endoscopic examination, that is from the edge of the ulcers and the nearby damaged zones for the former and at least 20 cm away from the affected areas for the latter. Two snap-frozen biopsies from healthy mucosa (possibly transverse colon) will be collected from each non-IBD patient. Viral DNA extraction will be performed by using the EZ1 DNA Tissue kit and EZ1Virus Mini Kit v2.0 (Qiagen, Hilden, Germany), while EBV DNA will be quantified by using the artus EBV QS-RGQ PCR Kit (Qiagen), and HCMV DNA will be quantified by using the artus CMV QS-RGQ kit (Qiagen), according to the manufacturer's instructions. Results will be expressed as IU/ml of blood and IU/10⁵ cells. Normalization of viral DNA load in tissue samples will be obtained by quantitative determination of β_2 -microglobulin gene. The lower detection limit is 1 DNA input target DNA copies (51). This analysis will be carried out at the the Molecular Virology Unit in Pavia.

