8.2 Analysis

Data will be described with the mean and standard deviation or the median and 25th-75th percentiles if continuous and as counts and percent if categorical. For the primary endpoint we will compute the prevalence as the ratio of the number of patients diagnosed with EBV infection to the number of patients evaluated, together with its 95%CI. We will use the Fisher exact test to compare the prevalence in UC patients to that of control. We will report the mean difference in proportions and its 95%CI. We will use binomial regression models with identity link (command binreg in Stata), to adjust for potential confounders, such as, but not limited to, age, gender, duration of disease and treatment. We will apply the 1:10 rule to adapt the number of confounders evaluated to the sample size. We will compare the prevalence of EBV infection between UC subgroups with the Fisher exact test (EP2a). In these cases, given in particular that the ratio of responders to non-responders is at yet unknown, we will compute *a posteriori* the power for the comparison. We will compute

sensitivity, specificity, area under the ROC curve and predictive values with 95% CIs for EP2b and EP2c. We will use the Spearman R and the Fisher exact test to assess the association, for continuous and categorical independent variables, respectively, with the dependent variables of EP2d to EP2h. All estimates will be presented with their 95% CI.

We will use Cox regression to assess the association of EBV infection with colectomy and of hospitalization for any cause; we will use Poisson regression to assess the association of EBV infection with the number of hospitalization from any cause. For secondary endpoints assessing associations, we will also fit regression models to adjust for possible confounders (as for the EP1) and report adjusted mean differences in proportions and 95% CI. We may also use propensity score inverse probability weights to account for the bias by indication when assessing treatment effect on the outcome.

The exploratory endpoints will be only descriptive.

We will use Stata 17 or later versions for computations. A 2-sided p-value <0.05 will be considered statistically significant. We will apply the Bonferroni correction for post-hoc comparisons.

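### The colectomy model compares any EBV infection with none, although the extended follow-up was added to compare patients with and without EBV colitis

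*Protocol*

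**What the plan says.** **The question.** Section 6 sets the aim of the study at 6 months and gives the reason for the optional visits at 9 and 12 months: they "will aid to understand if patients with superimposed EBV colitis undergo colectomy more frequently than patients without EBV colitis". The Summary says the same.

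**The endpoint and model.** Section 5.2.2 item i asks for the prognostic role of EBV infection on the 6- and 12-month outcome. Section 8.2 follows it: "We will use Cox regression to assess the association of EBV infection with colectomy". Section 7.1 defines the exposure of interest as EBV infection, meaning virus, viral protein or nucleic acid found in any fluid or tissue, with no load threshold.

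**The distinction.** Section 3 complains that infection and colitis have been used as if they were the same. It adds that a positive mucosal result does not by itself show end-organ disease, and it cites the group's own earlier work: "Indeed, we identified a cutoff of 1000 copies/100.000 cells as the value to distinguish a superimposed viral colitis". It also describes an intermediate group "carrying a mucosal viral load of between 100 and 1000 copies".

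**The units.** For the present study, section 7.1 states: "Results will be expressed as IU/ml of blood and IU/10⁵ cells". The detection limit in the same paragraph is given in copies. No conversion factor between copies and IU is given.

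**The concern.** The stated question and the fitted model use different exposures. A patient positive only in blood, or with a trace mucosal load, counts as exposed in the Cox model but would not be called EBV colitis on the distinction drawn in section 3.

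The interpretation of the longitudinal part is at stake. If such patients carry less colectomy risk than those with superimposed colitis, pooling them pulls the hazard ratio towards 1. A null result for any infection could then not be read as evidence that EBV colitis leaves colectomy risk unchanged, and that is the question the extra six months were added to address.

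**Working it through.** Section 8.1 gives precision and power for the prevalence comparison only, so there is no colectomy figure to reproduce. The check is mainly one of definitions.

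**1. Who falls on which side.** Divide the UC patients with follow-up into three groups:

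- A: EBV colitis (mucosal load above a cut-off)
- B: infected, but below the cut-off or positive in blood only
- C: EBV-negative

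| Place in protocol | Contrast |
|---|---|
| Summary and section 6, reason for 9- and 12-month visits | A versus B + C |
| 5.2.2 item i; 8.2 Cox model; 7.1 exposure definition | A + B versus C |

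Group B changes sides. No endpoint, study definition or model in the protocol isolates A. Viral load as a quantity enters only item d of 5.2.2, against endoscopic damage.

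**2. Direction of the effect.** Let s be the share of infected patients in group A, and let HR_A and HR_B be hazard ratios against C. For uncommon events, approximately:

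HR(any infection) = s × HR_A + (1 − s) × HR_B

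The documents give none of these inputs. Assume HR_A = 3:

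| s | HR_B = 1 | HR_B = 2 | HR_B = 3 |
|---|---|---|---|
| 25% | 0.25×3 + 0.75×1 = 1.5 | 0.25×3 + 0.75×2 = 2.25 | 3 |
| 50% | 2.0 | 2.5 | 3 |
| 75% | 2.5 | 2.75 | 3 |

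The dilution runs from a halving of the ratio (3 to 1.5) to none, depending mostly on HR_B.

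**3. Why group B should stand alone.** Simply switching to A versus everyone else is also diluted if B is at raised risk. With 30% infected, s = 50% and HR_B = 2 (assumptions), there are 15 patients in B and 70 in C per 100. The reference group's average hazard relative to C is (15×2 + 70×1)/85 = 1.18, so A versus the rest gives 3/1.18 = 2.5, not 3.

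**4. Precision.** Schoenfeld's approximation is power = Φ(√(d·p(1−p))·|ln HR| − 1.96), with d colectomies and exposed share p. Assume 30% infected, HR_A = 3 and HR_B = 1. The event counts are also assumptions.

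| Colectomies | Exposure | s = 25% | s = 50% | s = 75% |
|---|---|---|---|---|
| 10 | any infection | 9% | 17% | 26% |
| 10 | EBV colitis versus rest | 15% | 24% | 31% |
| 20 | any infection | 13% | 30% | 47% |
| 20 | EBV colitis versus rest | 25% | 42% | 54% |

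With d = 10 and p = 0.15, the standard error of ln HR is 1/√(10×0.15×0.85) = 0.886. An observed ratio of 3 would have a 95% CI of about 3/5.7 to 3×5.7, that is 0.5 to 17. Events may also be scarcer than 100 UC patients suggest, because Appendix 3 schedules follow-up for active UC only and Appendix 4 gives patients in remission a baseline assessment only.

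**5. Units.** The cut-off and the planned tissue result share a denominator (10⁵ cells) and differ in the numerator. If one copy were 0.2 to 5 IU (assumption), 1000 copies would correspond to 200 to 5000 IU per 10⁵ cells.

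**The case against.** The plan is consistent along its operative line. The general objective, the endpoint, the exposure definition and the Cox model all say EBV infection, and section 3 cites earlier literature linking infection, not colitis, to colectomy. The EBV-colitis question appears only as a rationale for optional visits, and the aim is placed at 6 months. An SAP, which is not at hand, might define EBV colitis.

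Most of this stands and limits the point. A reader might infer four stronger things that the documents do not support:

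- **That the unit mismatch breaks a planned analysis.** The cut-off is an earlier result reported in the background and is not adopted as a study definition. The one planned analysis of load as a quantity uses rank correlation or the Fisher test, and a fixed conversion factor would not change ranks. The gap matters only once the cut-off is used.
- **That section 8.2 abandons an EBV-colitis endpoint.** No such endpoint was ever set.
- **That the contradiction extends to hospitalisation.** The EBV-colitis question is posed for colectomy only.
- **That the dilution has a known size.** Any figure needs a load distribution and group risks that the documents do not give. A large loss requires low-load carriers to have nearly the risk of EBV-negative patients, while section 3 treats the intermediate band as calling for caution.

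What does not stand is that the matter is only a detail left to the SAP. The protocol names the exposure, and it is not the one in its stated question. Rewording the rationale would remove the contradiction but leave that question unexamined.

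**Conclusion.** The point holds as a mismatch between the stated purpose of the extended follow-up and the exposure in 5.2.2 item i and 8.2. Followed as written, the plan never estimates colectomy risk in EBV colitis against no EBV colitis. This rests on the text alone.

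Dilution of the any-infection estimate is conditional on group B carrying less risk than group A. Its size cannot be derived from the protocol, and the range of 1.5 to 3 for an assumed true ratio of 3 is illustration only. The question is not beyond reach, since quantitative mucosal load at baseline is already planned, centrally measured and normalised to cells. The answer will be imprecise under either exposure.

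**What to change.** - **5.2.2 item i and 8.2:** keep any EBV infection as the exposure. Add, for colectomy only, a pre-specified EBV-colitis exposure based on baseline mucosal load. Show three groups (EBV colitis, infected without EBV colitis, EBV-negative) so that infected patients below the cut-off are not merged with EBV-negative patients. State which biopsy supplies the load, because 7.1 samples inflamed and non-inflamed mucosa.
- **7.1:** if the previously published 1000 copies per 10⁵ cells is adopted for this analysis, state the laboratory's copies-to-IU factor or report both units.
- **Reporting:** give the EBV-colitis contrast as an estimate with its 95% CI, not as a powered test.

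The cost is wording in these sections and one derived variable from data already being generated, with no new samples or visits. The downside is a small exposed group with few colectomies, and hence a wide interval.

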4 RATIONALE OF THE STUDY

The role and the appropriate management of EBV infection in UC are the object of a wide debate. Therefore, the possibility to carry out a multicenter study aimed at assessing the true prevalence, the best diagnostic tool, the risk factors and the role of EBV infection in UC is expected to be of meaningful clinical value in the decisional algorithm for the correct management of this condition.

5 OBJECTIVES OF THE STUDY

5.1 General objectives

The main study objective is to evaluate the true prevalence of EBV infection in a cohort of UC patients in comparison with a cohort of non-IBD patients. In parallel, the identification of the more accurate diagnostic approach, the association with clinical and endoscopic indexes of activity, as well as the risk factors will be evaluated. Finally, the outcome of these patients will be assessed to establish the correct prognosis and relationship with EBV infection.

5.2 End-points

5.2.1 Primary endpoint

Evaluation of the prevalence of EBV infection, defined as isolation of the EBV or detection of viral proteins or nucleic acids in any body fluid or tissue specimens, in patients suffering from UC. The same analyses will be performed in a comparable cohort of non-IBD patients who undergo lower endoscopy during their work-up for irritable bowel syndrome (IBS) and microscopic colitis (as stated above). The parallel assessment of the HCMV load will avoid false interpretation of the role of EBV.

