2 STUDY FLOW CHART FOR ACTIVE ULCERATIVE COLITIS PATIENTS

3 BACKGROUND AND INTRODUCTION

- ❖ Inflammatory bowel disease (IBD), namely Crohn's disease and ulcerative colitis (UC), are emerging chronic and disabling enteropathies triggered and sustained by a dysregulated immune response towards antigens of the gut microbiota in genetically susceptible individuals (1,2). The growing use of immunosuppressive therapies, mainly based on biological agents, to achieve mucosal healing and prevent disease progression (3), has led to an increased risk of opportunistic infections (4,5,6), including that caused by the Epstein-Barr virus (EBV) (7). In this regard, although a considerable number of studies support the notion that colonic involvement through opportunistic viral infection in existing IBD is associated with a worsening of symptoms, increased prevalence of refractoriness and surgical intervention [8,9,10,11], the role played by EBV in UC, whether contributor or innocent bystander, remains a topic of ongoing controversy [12,13]. EBV infection is usually acquired early in the life and is generally asymptomatic in healthy people where it establishes a lifelong latency in target cells (memory B-cells) (14), while it reactivates in case of reduced host immunity (15). EBV, indeed, exists in two possible states of its life cycle, latent and lytic (16,17,18). The latter usually occurs in immunocompromised hosts where it eventually results in systemic or end-organ diseases leading to increased morbidity and mortality (19). Localizing in the gastrointestinal tract (20,21) represents a clinical challenge in IBD since it becomes hard to distinguish between a superimposed viral colitis and a relapse of the underlying disease. In this regard, the ECCO guidelines state that: "*Screening for EBV infection (through the search of specific anti-virus immunoglobulin) before initiation of immunomodulator therapy should be considered. In severe primary clinical EBV infection during immunomodulator therapy, antiviral therapy may be considered and immunomodulator therapy discontinued. In the event of EBV-driven lymphoproliferative disease during immunomodulator therapy, the patient should be managed in conjunction with appropriate specialists. Immunomodulators should be stopped*" (22). It appears clear that the main focus is lymphoma-driven (23), with almost no mention of secondary symptomatic infection due to reactivation of the lytic phase of the virus life cycle, that is the most frequent condition in clinical practice. As a consequence, several crucial points still remain unsolved, such as its true prevalence and role in tissue damage, the best diagnostic and therapeutic approach, as well as the identification of risk factors still remains elusive.

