ability to affect cytokine production (20) may account for how it escapes host immune surveillance directly at mucosal level. Here, resting memory B cells serve as the long-term reservoir of latent EBV infection, and their differentiation into plasma cells in response to inflammatory stimuli may trigger the lytic phase and subsequent release of viral particles (38), leading to viral replication (15,16,17). Moreover, T-cell action in controlling viral replication (18) may be hampered by concurrent malnourishment and immunosuppressive drugs, thus resulting in an uncontrolled activation of the lytic phase of the viral life cycle which localizes precisely in the target organ (21).

- ❖ Therefore, we aim to carry out a multicenter interventional without drug and medical device study in order to definitely prove whether EBV infection represents a causative factor in tissue damage or a surrogate marker of severe colitis (13), an issue that may greatly contribute to understanding the mutual relationship between the host and the virus and to correctly manage the patients. The parallel analysis of the Human Cytomegalovirus (HCMV) load will assure a better understanding of the role of EBV. The possibility to involve the IG-IBD Centers gives the assurance for the study feasibility. Furthermore, the presence of clinicians with high expertise on histologic examination of IBD samples (Doctor [name]) and opportunistic viral infections ([name]) gives more strength to the proposal. We thus intend to recruit patients suffering from UC, either naïve to therapy or under treatment (both responders and non-responders) and non-IBD controls in order to evaluate the real prevalence, role and risk factors of EBV infection in this peculiar clinical setting. Moreover, by using qRealTime-PCR and ISH in parallel, we want to definitely establish the better diagnostic tool. Finally, the duration of three years seems the right length of the study to recruit a sizable number of patients and evaluate their outcome, as well as to perform the analysis and interpretation of results.

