7.1 General design

- ❖ *Type:* cross-sectional study with a longitudinal component.
- ❖ *Description of the exposure of interest:* EBV infection, defined as isolation of the EBV or detection of viral proteins or nucleic acids in any body fluid or tissue specimens.
- ❖ *Description of the matching factor(s) and how the matching will be done:* Center, sex- and age (5 year classes)-matching will be performed among the IBD patients and concomitant non-IBD control subjects.
- ❖ *Methods used to minimize bias.* The assessment of EBV infection through qRealTime-PCR, histology or ISH as primary endpoint is *per se* unbiased due to standardization and reproducibility of the techniques applied. Also calculation of clinical and endoscopic indexes of activity are routinely applied in IG-IBD centres. Moreover, the measurement of exploratory endpoints will be assessed by blinded technicians, whereas monitoring of patients' outcome will be performed by the local Principal Investigator.
- ❖ *Describe the strategy/process by which participants will be recruited, screened, and enrolled in the study.* All cases admitted at each IG-IBD center that agrees to participate in this study will be screened for inclusion. All enrolled cases undergo lower endoscopy with mucosal sampling from both inflamed and non-inflamed mucosa in each IBD patient and from healthy mucosa in each control subject, as part of their diagnostic workup for disease diagnosis, relapse or follow-up. Patients' assessment includes: clinical examination, body mass index calculation, evaluation of smoking habits and stratification according to the Montreal classification (44), routine laboratory tests, and calculation of clinical [SCCAI (45)] and endoscopic [UCEIS (46,47)] indexes of activity.
- ❖ All enrolled cases also undergo peripheral blood harvest. Quantitation of viral DNA load will be performed on both peripheral blood samples and whole mucosal specimens by means of qRealTime-PCR (50). In addition, mucosal specimens will be also evaluated by ISH.

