8 STATISTICAL CONSIDERATIONS

8.1 Sample size

Sample size has been calculated based on the primary endpoint, i.e., the prevalence of EBV infection in UC patients. In UC patients non-responders to standard of care the prevalence of EBV is expected around 50%; in UC patients responders to conventional treatment may be around 10%. We hypothesize that the prevalence of EBV infection in the control population is around 0-1%. Based on the feasibility on enrolment given study design, we plan to enroll about 100 UC patients. ~~The precision achieved with 100 patients is replicated. However, the power achieved when comparing 100 patients and 100 controls is not replicated; according to our computations is much larger than that reported by the Authors (76.9% rather than 27% with a prevalence of 10% and 99.8% rather than 87% with a prevalence of 20%).~~

Prevalence	95%CI	precision	power to detect difference from control
50%	40% - 60%	10%	100%
30%	21% - 40%	9%	100%
20%	13% - 29%	8%	99,8%
10%	5% - 18%	6%	76,9%

The power to detect a significant difference with the Fisher exact test from an expected proportion in controls of 1% is above 80% for proportions of infection of 10% or greater, considering 100 patients in each group and an alpha level of 5%. Calculations are performed using Stata 17 (StataCorp, College Station, TX, USA).

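### The primary endpoint counts any EBV detection in any specimen, blood included, but the 0-1% control prevalence behind the stated power is supported only by a finding in mucosal epithelial cells

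*Protocol*

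**What the plan says.** Section 5.2.1 takes as primary endpoint how common EBV infection is among UC patients. Infection is "defined as isolation of the EBV or detection of viral proteins or nucleic acids in any body fluid or tissue specimens". Section 7.1 repeats the definition as the exposure of interest. Neither place names a primary specimen, a viral load or a phase of the viral cycle.

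Section 7.1 measures EBV DNA in every patient and control "on both freshly collected whole peripheral blood samples and endoscopic specimens harvested from colonic mucosa". On the assay it says: "The lower detection limit is 1 DNA input target DNA copies". Mucosa is also examined by ISH for EBER, which Section 5.2.3 describes as usually a latency marker.

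Section 3 says that EBV is usually acquired early in life and is generally silent in healthy people, "where it establishes a lifelong latency in target cells (memory B-cells"). It adds that, at mucosal level, "resting memory B cells serve as the long-term reservoir of latent EBV infection". On the meaning of a positive mucosal PCR it warns that "a positive result does not necessarily imply that the patient is suffering from an EBV-related end-organ disease", and it reports a cut-off of 1000 copies per 100,000 cells for superimposed viral colitis.

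Section 8.1 then states: "We hypothesize that the prevalence of EBV infection in the control population is around 0-1" per cent. All power figures use 1%.

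**The concern.** The definition and the control assumption do not rest on the same measurement. Under the definition, a control with any EBV DNA in whole blood or in a whole biopsy is infected. Whole blood contains the cells that Section 3 names as the site of lifelong latency, and Section 3 places the same reservoir in the mucosa. The one finding in the text that supports near-zero controls is narrower. It is the earlier report in Section 3 of EBV DNA in epithelial cells of diseased UC mucosa but not of healthy mucosa from non-IBD controls. That finding says nothing about blood, or about B cells within a whole biopsy.

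Two things are at stake. Carriage counted in both groups narrows the UC-control difference and moves both proportions away from zero, where the variance is larger, so power falls. The result also becomes harder to read, because a positive patient may be a latent carrier rather than someone with the mucosal infection that the rationale addresses. The same variable feeds most of the secondary association analyses in Section 5.2.2.

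**Working it through.** **Inputs.** 100 per group, alpha 5%, control 1%, UC 10, 20, 30 and 50% (Section 8.1); two-sided Fisher exact test (Section 8.2). The rate c at which latent carriage is detected is not in the protocol. It is an assumption, varied below.

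**Step 1: the plan's own figures.** Power is the sum, over all pairs of counts (x, y) that the Fisher test rejects, of Bin(x; 100, p_UC) × Bin(y; 100, p_control). At control 1% this gives 100%, 100%, 99.8% and 76.9% for UC 50, 30, 20 and 10%. The table in Section 8.1 reproduces. The exact intervals also match: 39.8-60.2, 21.2-40.0, 12.7-29.2 and 4.9-17.6%. The arithmetic is sound; the open question is the 1% input.

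**Step 2: carriage in both groups.** If carriage is detected with probability c, independently of the infection that the plan had in mind, each group's positive rate becomes

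p* = 1 − (1 − p)(1 − c),

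and the difference shrinks to (1 − c)(p_UC − p_control). For c = 5%:

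- control: 1 − 0.99 × 0.95 = 5.95%
- UC 10%: 1 − 0.90 × 0.95 = 14.5%
- difference: 0.95 × 9 = 8.55 points, against 9 planned.

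Most of the loss therefore comes from the higher variance, not from the smaller gap.

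| Carriage c | Control p* | UC 10% | UC 20% | UC 30% | UC 50% |
|---|---|---|---|---|---|
| 0 (as stated) | 1.0% | 76.9% | 99.8% | 100% | 100% |
| 5% | 5.95% | 43.2% | 94.6% | 99.9% | 100% |
| 10% | 10.9% | 30.0% | 83.8% | 99.1% | 100% |
| 20% | 20.8% | 17.4% | 61.2% | 92.6% | 100% |
| 30% | 30.7% | 12.1% | 43.5% | 80.4% | 99.8% |

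(Cells are power; the UC column heads are prevalences before carriage is added.)

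**Step 3: precision.** The interval for the UC prevalence depends only on 100 and the observed proportion. The control rate does not enter, so the precision column stands.

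**The case against.** The strongest reply is that nothing in the protocol shows controls to be positive more often than 1%. Latency in memory B cells is not the same as detectability in a blood aliquot or two biopsies. The one-copy limit is an analytical figure per reaction, not a per-patient detection rate. This stands. A reader might infer that the definition and the 0-1% figure are incompatible, but the documents do not support that: they leave a gap in justification, not a proven contradiction.

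A reader might also hold the UC rate fixed and raise only the controls. Power for UC 20% then falls to 44.4% at control 10%, and for UC 10% to 19.0% at control 5%. That treats the UC figures as already including carriage, which Section 8.1 does not say, and it leaves out that carriage raises both groups. The milder losses in the table above follow from the mechanism itself.

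It can also be said that the sample size was set by feasibility and that precision is tabulated beside power. True: it is the power statement, not the whole basis for 100 patients, that lacks support.

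Lastly, a reader might want 100 or 1000 copies as the definition of infection. Section 3 offers 1000 copies as a marker of colitis and the range from 100 to 1000 as a band for caution, and it criticises the mixing of infection with colitis. Leaving the cut-offs out of an infection endpoint is consistent with that. Load, blood against mucosa, ISH against PCR and cycle phase are separate endpoints already, so the data are not lost. None of this supplies a source for 0-1% in blood.

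**Conclusion.** The concern holds as a mismatch between the endpoint and the input to its power. The endpoint includes whole blood and can register latent carriage, while the control rate is supported in the text only for mucosal epithelial cells. The stated power is therefore unjustified for the endpoint as written.

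The size depends on the assumed carriage rate and on its adding independently to both groups. At 5-20% carriage, power is 43.2-17.4% instead of 76.9% for UC 10%, and 94.6-61.2% instead of 99.8% for UC 20%. If the true UC prevalence is 30-50%, power stays above 80% up to 30% carriage, and the problem is then mainly one of interpretation.

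**What to change.** - In Sections 5.2.1 and 7.1, define primary positivity as EBV DNA detected by qPCR in baseline colonic mucosa. This is the specimen type closest to the source of the 0-1% figure.
- Report blood PCR and ISH positivity separately, and keep any detection in any specimen as a sensitivity analysis.
- Add a supportive analysis of probable EBV colitis at the protocol's own 1000 copies per 100,000 cells. Section 7.1 reports in IU, so fix the conversion before analysis. This is not the definition of infection.
- Restate the power column in Section 8.1 over control prevalences of about 1-10%. Whole biopsies also contain B cells, so 0-1% remains an assumption even in mucosa.

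The cost is wording and a revised table; every assay is already planned. The downside is that the mucosal prevalence can be no higher than the any-specimen figure, and the stated power becomes less favourable. If the sponsor prefers to keep any detection as primary, it should give a control rate that covers blood and recompute the power from it.
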